9.3.4. Exploratory/subgroup analysis

Subgroup analyses for the primary endpoints will be conducted to assess consistency of the intervention effect across the following subgroups:

- Participating country
- Immediate entry in the severe group: yes vs no (only EU-SolidAct Part B)
- Age group: < 65 vs \geq 65 years
- Sex: female vs male
- Duration of symptoms prior to enrolment (\leq 7 days, 8-14 days, >14 days)
- Prior vaccination for COVID-19: yes vs no
- Mechanically ventilated/on ECMO vs not at baseline

In addition, subgroup analyses on use of certain therapeutic drug components of the standard of care will be considered, especially if the standard of care changes during the trial.

If the number of participants is too small (less than 10%) within a subgroup, then the subgroup categories may be redefined before locking the database. Further details on the statistical analysis or additional subgroup analyses will be provided in the SAP.

9.3.5. Safety analyses

Safety endpoints include serious adverse events (SAEs) leading to study treatment discontinuation and death. SAEs will be coded using the current version of the Medical Dictionary for Regulatory Activities (MedDRA). SAEs leading to study treatment discontinuation and death will be summarized with number and proportion. More details on the statistical analysis will be provided in the SAP.

9.3.6. Other analyses

All outcomes relative to the modular secondary objective will be summarized with the appropriate descriptive statistic. Outcomes will be compared between each study intervention group and the control using the appropriate statistical test. More details on the statistical analysis will be provided in the SAP.

9.4. Interim Analysis

No formal interim analysis for efficacy will be done. However, an independent data monitoring committee (DMC) consisting of independent scientists not otherwise involved in the trial has been appointed and will review the data regularly during the study for safety and scientific integrity and will make recommendations to the sponsor regarding the stopping of an intervention for harm or for futility. The frequency of the committee data review meetings and other aspects such as stopping rules will be detailed in a separate charter and possibly in the statistical analysis plan depending on the safety profile of the study intervention(s). There will only be one DMC overseeing all trial arms, and this committee will communicate with the DMCs of other corresponding platform trials to exchange information. The level of monitoring will depend on the safety profile of the intervention.

9.5. Sample Size Determination

9.5.1. Phase 3 General Considerations

In the DisCoVeRy (NCT04315948) and Nor-Solidarity (NCT04321616) trials, the proportion of patients with moderate disease at inclusion in achieving disease progression at day 14 and those with severe disease in achieving death at day 60 are shown in

Table 9.1 below.

Table 9.1 Event rate on SoC patient in Discovery and Nor-Solidarity trials

	Discovery	Nor- Solidarity	Nor-Solidarity
	(included: July- October 2020)	(included before 1st July 2020)	(included after 1st July 2020)
14-day rate of progression in moderate patients	13.1% [7.5-22.4]	13.5% [9.8-22.8]	20.5% [7.6-31.5]
28-day mortality in severe patients	9.7% [3.7-24.3]	5.1% [1.4-8.8]	9.1% [0.2-17.2]

According to numbers published by Santé publique France on December 29, 2020 there were 770 deaths out of 4411 (17.5%) patients admitted in ICU in France, suggesting a slightly higher rate compared to the autumn numbers in Discovery and Nor-Solidarity.

Based on these data, we assumed a cumulative probability of disease progression of 15% at 14 days in the SoC group for Part A (moderate disease) and mortality at 15% at 60 days for Part B (severe disease).

The sample size and power calculations were made using the statistical software package nQuery Advanced, using the two sample Log-Rank test module (Version 8.6.1.0), based on the primary efficacy estimand and its endpoint. The results are presented in Table 9.2 and Table 9.3 below.

Assuming a 15% progression for the SoC group in Part A and a 2-sided type-1 error rate of 5% and using the Log-Rank test, the study will have over 90% power under a sample size of 924, 521 and 378 per arm to detect a treatment difference of 5%, 6.5% and 7.5% respectively. We hypothesize that a treatment difference in progression rates at day 14 of 5% seems achievable. Therefore, we plan to enrol 950 participants per arm, considering potential dropouts before the assessment of the primary endpoint at day 14.

Table 9.2: Sample size calculation for EU-SolidAct Part A superiority trial

	Scenario 1	Scenario 2	Scenario 3
Outcome (Disease progression at day 14)			
Hypothesized event rate with SoC	15%	15%	15%
Expected event rate with intervention	10%	8.5%	7.5%
Type I error (two-sided)	0.05	0.05	0.05
Power	90%	90%	90%
Hazard ratio (HR)	0.648	0.547	0.48
N per group	924	521	378
Total number of events required	224	115	78

Similarly, assuming a 15% mortality for the SoC group in Part B and a 2-sided type-1 error rate of 5% and using the Log-Rank test, the study will have over 90% power with a sample size of 924, 521 and 378 per arm to detect a treatment difference of 5%, 6.5% and 7.5% respectively. We hypothesize that a treatment difference in mortality rates at day 61 of 5% seems achievable. Therefore, we plan to enrol 950 participants per arm, considering potential drop-outs before the assessment of the primary endpoint at day 61

Table 9.3: Sample size calculation in EU-SolidAct Part B superiority trial

	Scenario 1	Scenario 2	Scenario 3
Outcome (Death at day 61)			
Hypothesized event rate with SoC	15%	15%	15%
Expected event rate with intervention	10%	8.5%	7.5%
Type I error (two-sided)	0.05	0.05	0.05
Power	90%	90%	90%
Hazard ratio (HR)	0.648	0.547	0.48
N per group	924	521	378
Total number of events required	224	115	78

In case combination therapies are assessed by factorial design, the main assumption will be that no interaction exists between the treatments and therefore no modification of the sample size will be necessary. If synergies or effect modifications between treatments are of interest, the intervention-specific sub-protocols will define the sample size needed for detecting the interaction effect.

For a non-inferiority trial, assuming a 15% primary endpoint rate (progression in Part A and mortality in part B) in the active comparator arm, a non-inferiority margin of 3%, a 95%

confidence interval of the effect size and a 90% power, we need to enrol 3000 participants per arm

9.5.2. Phase 2 General Considerations

Based on unpublished data from 8500 patients with COVID-19 as described in the RECOVERY protocol (<https://www.recoverytrial.net/files/recovery-protocol-v14-0-2021-02-15.pdf>), assuming a mean (standard deviation) SF-ratio of 3.3 (1.7) at day 5, and a correlation between an individual's baseline and day 5 SF-ratio of 0.5, randomization of 400 participants will provide 90% power at a two-sided 5% significance level to detect a difference in SF-ratio of 0.5 (the chosen minimum clinically meaningful difference [which is similar to the difference in 1 point on the WHO ordinal scale]), even if 10% of participants discontinue study treatment before day 5.

10. Supporting Documentation and Operational Considerations

10.1. Appendix 1: Regulatory, Ethical, and Study Oversight Considerations

10.1.1. Regulatory and ethical considerations

- This study will be conducted in accordance with the protocol and the following:
 - Consensus ethical principles derived from international guidelines including the Declaration of Helsinki and Council for International Organizations of Medical Sciences (CIOMS) international ethical guidelines
 - Applicable ICH Good Clinical Practice (GCP) guidelines
 - Applicable laws and regulations

The protocol, protocol amendments, ICF, investigator's brochure and other relevant documents (eg, advertisements) must be submitted to an IRB/IEC by the investigator and reviewed and approved by the IRB/IEC before the study is initiated.

Any amendments to the protocol will require IRB/IEC approval before implementation of changes made to the study design, except for changes necessary to eliminate an immediate hazard to study participants.

Protocols and any substantial amendments to the protocol will require health authority approval prior to initiation except for changes necessary to eliminate an immediate hazard to study participants.

The investigator will be responsible for the following:

- Providing written summaries of the status of the study to the IRB/IEC annually or more frequently in accordance with the requirements, policies, and procedures established by the IRB/IEC
- Notifying the IRB/IEC of SAEs or other significant safety findings as required by IRB/IEC procedures
- Providing oversight of the conduct of the study at the site and adherence to requirements of ICH guidelines, the IRB/IEC, European regulation 536/2014 for clinical studies (if applicable), European Medical Device Regulation 2017/745 for clinical device research (if applicable), and all other applicable local regulations

10.1.2. Financial Disclosure

Investigators and sub-investigators will provide the sponsor with sufficient, accurate financial information as requested to allow the sponsor to submit complete and accurate financial certification or disclosure statements to the appropriate regulatory authorities. Investigators are responsible for providing information on financial interests during the course of the study and for 1 year after completion of the study.

10.1.3. Informed Consent process

The investigator or his/her representative will explain the nature of the study, including the risks and benefits, to the participant, their legally authorized representative (LAR) or relative and answer all questions regarding the study.

If the patient is unable to give consent due to the severity of their medical condition (e.g., acute respiratory failure or need for immediate ventilation) or prior disease, then consent may be obtained from a close relative acting as the participant's designated representative or, if a suitable relative is not immediately available, an independent doctor. Further consent will then be sought with the participants if they recover sufficiently or with the designated representative at the earliest opportunity (continuation consent).

If the patient is unable to give consent due to the severity of their medical condition or if hospital visiting rules or parental infection mean a relative or legally authorized representative cannot be physically present, witnessed consent may be obtained over the telephone or web video link.

Participants must be informed that their participation is voluntary. Participants, their LAR or their designated representative (relative) will be required to give a statement of informed consent that meets the requirements, local regulations, ICH guidelines, privacy and data protection requirements, where applicable, and the IRB/IEC or study centre.

The medical record must include a statement that informed consent was obtained before the participant was enrolled in the study, the nature of consent (participant, LAR, designed representative or independent doctor), and the date the consent was obtained. The authorized person obtaining the informed consent must also sign the ICF. In case of urgent oral consent is obtained it should be written in medical record. This refers to countries in which according to their national drug law oral consent under such circumstances are allowed to be given.

Participants must be reconsented to the most current version of the ICF(s) during their participation in the study if relevant.

A copy of the ICF must be provided to the participant, their legally authorized representative or their designated representative. The ICF (including patient information and data protection statement) will be translated into the languages of the participating countries in this trial.

Participants who are rescreened are required to provide a new informed consent.

The ICF will contain a separate section that addresses the use of remaining samples for optional exploratory research. The investigator or authorized designee will explain to each participant the objectives of the exploratory research. Participants will be informed that they are free to refuse participation and may withdraw their consent at any time and for any reason during the storage period. A separate signature will be required to document a participant's agreement to allow remaining specimens to be used for exploratory research. Participants who decline to participate in this additional research will not provide this separate signature.

10.1.4. Data protection

Participants will be assigned a unique identifier by the sponsor. Any participant records or datasets that are transferred to the sponsor will contain the identifier only; participant names or any information which would make the participant identifiable will not be transferred.

The participant must be informed that his/her personal study-related data will be used by the sponsor in accordance with local data protection law. The level of disclosure must also be explained to the participant who will be required to give consent for their data to be used as described in the informed consent

The participant must be informed that his/her medical records may be examined by Clinical Quality Assurance auditors or other authorized personnel appointed by the sponsor, by appropriate IRB/IEC members, and by inspectors from regulatory authorities.

10.1.5. Committees structure**Trial Steering Committee**

The Trial Steering Committee is responsible for:

- (i) Agreement of the final Protocol and the Data Analysis Plans;
- (ii) Reviewing progress of the study and, if necessary, deciding on Protocol changes;
- (iii) Review and approval of study publications and sub-study proposals;
- (iv) Reviewing new studies that may be of relevance.

Data Monitoring Committee

The independent Data Monitoring Committee is responsible for:

- (i) Reviewing unblinded interim results according to the protocol;
- (ii) Advising the Steering Committee if, in their view, the randomized data provide evidence that may warrant a change in the protocol (e.g., modification or cessation of one or more of the treatment arms).

Central Coordinating Office (CCO)

The CCO is responsible for the overall coordination of the study, including:

- (i) Study planning and organisation of Steering Committee meetings;
- (ii) Ensuring necessary regulatory and ethics committee approvals;
- (iii) Development of Standard Operating Procedures and computer systems;
- (iv) Monitoring overall progress of the study;
- (v) Provision of study materials to regional or local coordinating centres (RCCs/LCCs);
- (vi) Monitoring and reporting safety information in line with the protocol and regulatory requirements;
- (vii) Dealing with technical, medical and administrative queries from LCCs.

Regional/Country specific Coordinating Centre (RCC)

The RCCs are responsible for:

- (i) Ensuring necessary regulatory and ethics committee approvals;
- (ii) Provision of study materials to LCCs;
- (iii) Dealing with technical, medical and administrative queries from LCCs.

Local Clinical Centres (LCC)

The LCC lead investigator and LCC clinic staff are responsible for:

- (i) Obtaining all relevant local permissions (assisted by the CCO);
- (ii) All trial activities at the LCC, including appropriate training and supervision for clinical staff;
- (iii) Conducting trial procedures at the LCC in line with all relevant local policies and procedures;
- (iv) Dealing with enquiries from participants and others.

10.1.6. Data quality assurance

- All participant data relating to the study will be recorded on electronic CRFs unless transmitted to the sponsor or designee electronically (e.g., laboratory data) via secure platform transfer or encrypted email. The investigator is responsible for verifying that data entries are accurate and correct by physically or electronically signing the CRF.
- Guidance on completion of eCRFs will be provided in the Trial Master File.
- The investigator must permit study-related monitoring, audits, IRB/IEC review, and regulatory agency inspections and provide direct access to source data documents.
- Monitoring details describing strategy, including definition of study critical data items and processes (eg, risk-based initiatives in operations and quality such as risk management and mitigation strategies and analytical risk-based monitoring), methods, responsibilities, and requirements, including handling of noncompliance issues and monitoring techniques (central, remote, or on-site monitoring) are provided in the monitoring plan.
- The sponsor or designee is responsible for the data management of this study, including quality checking of the data.
- The sponsor assumes accountability for actions delegated to other individuals (e.g., contract research organizations).
- Records and documents, including signed ICFs, pertaining to the conduct of this study must be retained by the investigator for 15 years after study completion unless local regulations or institutional policies require a longer retention period. No records may be destroyed during the retention period without the written approval of the sponsor. No records may be transferred to another location or party without written notification to the sponsor.

10.1.7. Source documents

- Source documents provide evidence for the existence of the participant and substantiate the integrity of the data collected. Source documents are filed at the investigator's site.
- Data entered in the eCRF that are transcribed from source documents must be consistent with the source documents or the discrepancies must be explained. The investigator may need to request previous medical records or transfer records, depending on the study. Also, current medical records must be available.

- Definition of what constitutes source data, and its origin can be found in monitoring guidelines.
- The investigator must maintain accurate documentation (source data) that supports the information entered in the eCRF.
- Study monitors will perform ongoing source data verification to confirm that data entered into the eCRF by authorized site personnel are accurate, complete, and verifiable from source documents; that the safety and rights of participants are being protected; and that the study is being conducted in accordance with the currently approved protocol and any other study agreements, ICH GCP, and all applicable regulatory requirements.

10.1.8. Study and site start and closure

First Act of Recruitment

- The study start date is the date when the clinical study will be open for recruitment of participants.
- The first act of recruitment is the informed consent and will be the study start date.

Study/Site Termination

- Study sites will be closed upon study completion. A study site is considered closed when all required documents and study supplies have been collected and a study-site closure visit has been performed.
- The investigator may initiate study-site closure at any time, provided there is reasonable cause and sufficient notice is given in advance of the intended termination.
- Reasons for the early closure of a study site by the sponsor or investigator may include but are not limited to:
 - Failure of the investigator to comply with the protocol, the requirements of the IRB/IEC or local health authorities, the sponsor's procedures, or GCP guidelines
 - Inadequate or no recruitment (evaluated after a reasonable amount of time) of participants by the investigator
 - Total number of participants included earlier than expected
- Reasons for early study termination by the sponsor may include but are not limited to:
 - Discontinuation of further study intervention development
 - Occurrence of AEs unknown to date in respect of their nature, severity and duration

- Medical or ethical reasons affecting the continued performance of the trial, including
 - external evidence indicating efficacy or harm of any of the study interventions
 - a general lack of eligible patients due to vaccination or other reasons

If the study is prematurely terminated or suspended, the sponsor shall promptly inform the investigators, the IECs, the regulatory authorities, and any contract research organization(s) used in the study of the reason for termination or suspension, as specified by the applicable regulatory requirements. The investigator shall promptly inform the participant and should assure appropriate participant therapy and/or follow-up.

10.1.9. Publication policy

The study will be registered in a public register, in which trial results will be posted. The results of this study will be published in a suitable publication irrespective of findings. Results will also be presented at scientific meetings.

The sponsor will comply with the requirements for publication of study results. In accordance with standard editorial and ethical practice, the sponsor will generally support publication of multicentre studies only in their entirety and not as individual site data. In this case, a coordinating investigator will be designated by mutual agreement.

Authorship will be determined by mutual agreement and in line with International Committee of Medical Journal Editors authorship requirements. Conflicts of interests will be disclosed. The contribution of ECRIN and its national partners will be fairly described in the acknowledgement section or as co-author, depending on the contribution in the trial design, planning and publication.

Individual patient-level data will be made as public as possible while maintaining the integrity and privacy of the trial participants. Anonymized data will be made publicly available using a data repository, including any programming code used to produce the trial results. De-identified data will be made available upon request and evaluation of the requestee's ability and willingness to maintain the integrity and privacy of the trial participants. Further details of data sharing will be given in a separate data sharing plan.

10.2. Appendix 2: Clinical Laboratory Tests and Biobanking

10.2.1. Clinical Laboratory Tests

The tests detailed in table 10.2.1 will be performed by the local laboratory.

Protocol-specific requirements for inclusion or exclusion of participants are detailed in section 5. of the protocol.

Additional tests may be performed at any time during the study as determined necessary by the investigator or required by local regulations.

Table 10.2.1: Protocol-required Safety Laboratory Tests

Laboratory Tests	Parameters
Haematology	
	Haemoglobin (g/dL)
	Platelet count ($\times 10^9/L$)
	White blood cell count ($\times 10^9/L$)
	Neutrophils ($\times 10^9/L$)
	Lymphocytes ($\times 10^9/L$)
Clinical chemistry	
	K, Potassium (mmol/L)
	Na, Sodium (mmol/L)
	Creatinine ($\mu\text{mol/L}$)
	Total bilirubin ($\mu\text{mol/L}$)
	INR, International normalized ratio
	ALT, Alanine aminotransferase or SGOT, serum glutamic-oxaloacetic transaminase (U/L)
	AST, Aspartate aminotransferase or SGPT, Serum glutamic-pyruvic transaminase (U/L)
	Glucose (mmol/L)
	D-dimer (mg/L FEU)
	Ferritin ($\mu\text{g/L}$)
	LDH, Lactate dehydrogenase (U/L)
	Amylase (U/L)
	Procalcitonin (ng/mL)

	CRP, C-reactive protein (mg/L)
Pregnancy testing	
	Highly sensitive serum human chorionic gonadotropin (hCG) pregnancy test (as needed for women of childbearing potential)

NOTES: Details of liver chemistry stopping criteria and required actions and follow-up are given in section [7.1.1. Liver Chemistry Stopping Criteria] and Appendix [5: Liver Safety: Suggested Actions and Follow-up Assessments [and Study Intervention Rechallenge Guidelines]]. All events of ALT [or AST] $\geq 3 \times$ upper limit of normal (ULN) and total bilirubin $\geq 2 \times$ ULN (> 35% direct bilirubin) or ALT [or AST] $\geq 3 \times$ ULN and international normalized ratio (INR) > 1.5 (if INR measured), which may indicate severe liver injury (possible Hy's law), must be reported to [sponsor] in an expedited manner (excluding studies of hepatic impairment or cirrhosis).

A woman is considered of childbearing potential (WOCBP), i.e. fertile, following menarche and until becoming post-menopausal unless permanently sterile. Permanent sterilisation methods include hysterectomy, bilateral salpingectomy and bilateral oophorectomy.

A postmenopausal state is defined as no menses for 12 months without an alternative medical cause. A high follicle stimulating hormone (FSH) level in the postmenopausal range may be used to confirm a post- menopausal state in women not using hormonal contraception or hormonal replacement therapy. However, in the absence of 12 months of amenorrhea, a single FSH measurement is insufficient.

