8.6.9. Disease-related Events (DREs) and/or Disease-related Outcomes not qualifying as AEs or SAEs

These events may refer to disease- or complication-related events that are common in Covid-19 patients and can be serious/life-threatening.

They are reported systematically on the eCRF in the pre-defined daily data sections. However, they will NOT be reported as SAE in the eCRF, even though the event may meet the definition of an SAE, unless the investigator considered that there is a reasonable possibility that the study intervention (blinded investigational agent/placebo or study-supplied SoC treatment) caused the event.

These events may occur during the initial hospitalization, lead to a re-admission, or occur in a later hospitalization during follow-up.

The DREs are given in Section 10.4 Appendix 4.

Some of these events can be recorded as AESI, depending on the IMP profile.

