10.4. Appendix 4: Disease-related Events (DREs)

- Hyper/Hypoglycaemia
- Anaemia
- Coagulation disorder
- Acute renal failure
- Pancreatitis
- Cardiac disorders: cardiac arrhythmia (cardiac flutter, cardiac fibrillation), cardiac ischemia, cardiac arrest, congestive heart failure
- Endocarditis / bacteraemia
- Myocarditis / pericarditis
- Severe Acute Respiratory Distress Syndrome (severe ARDS)
- Pneumothorax
- Pleural effusion
- Pulmonary embolism
- Arterial thrombosis
- Deep venous thrombosis
- Meningitis / Encephalitis
- Stroke / Cerebrovascular accident
- Liver dysfunction
- Bacterial pneumonia, including ventilator-associated pneumonia
- Coma / Confusion
- Gastrointestinal haemorrhage

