10.5. Appendix 5: Liver Safety: Suggested Actions and Follow-up Assessments

To be detailed in the intervention-specific sub-protocol(s).

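### The possible-Hy's-law reporting rule in Appendix 2 conflicts with the disease-related-event exemption, uses a bilirubin fraction that is not a required test, and sits under crossed ALT/AST synonyms

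*Protocol*

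**What the plan says.** **The rule.** The NOTES under Table 10.2.1 define possible severe liver injury by two limbs joined by an 'or'.

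- Bilirubin limb: ALT [or AST] at least 3 x ULN with total bilirubin at least 2 x ULN, qualified by "> 35% direct bilirubin".
- INR limb: ALT [or AST] at least 3 x ULN with "international normalized ratio (INR) > 1.5 (if INR measured".

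Every event meeting either limb "must be reported to [sponsor] in an expedited manner (excluding studies of hepatic impairment or cirrhosis".

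**Safety reporting.** Appendix 4 lists "Liver dysfunction" among the disease-related events. Section 8.6.9 says of such events that "they will NOT be reported as SAE in the eCRF, even though the event may meet the definition of an SAE", except where the investigator sees a reasonable possibility that the study intervention was the cause. Section 8.6.1 makes the same exception to immediate SAE reporting. Section 8.6.9 adds that some of these events can be handled as AESI, depending on the product.

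**Required tests.** Footnote 4 of the Schedule of Assessments and Table 10.2.1 both list total bilirubin, INR, ALT and AST. Neither lists direct bilirubin. Appendix 2 allows additional tests when the investigator finds them necessary.

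**Names.** Table 10.2.1 prints "ALT, Alanine aminotransferase or SGOT, serum glutamic-oxaloacetic transaminase (U/L", and pairs AST with SGPT in the next row.

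**Cross-reference.** The NOTES state: "Details of liver chemistry stopping criteria and required actions and follow-up are given in section [7.1.1. Liver Chemistry Stopping Criteria". Section 7 contains only 7.1, 7.2 and 7.3. Section 7.1 leaves intervention-specific stopping criteria to the sub-protocols, and Appendix 5 reads in full "To be detailed in the intervention-specific sub-protocol(s".

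**The concern.** A possible-Hy's-law rule is meant to bring a small number of important cases to the sponsor quickly and in the same way from every site. That needs a criterion that can be evaluated from data every site collects, and one unambiguous instruction on what to do when it is met.

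Hospitalised COVID-19 patients can have abnormal liver tests from the disease itself, which is presumably why liver dysfunction is on the disease-related list. So the cases the liver rule is written to catch are also cases an investigator may attribute to the disease. In the one sub-protocol summarised (10.8.1) the trial is double blind, so that attribution is made without knowing the treatment.

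What depends on it is the second look. Under section 8.6.6 the Trial Safety Group reviews the SAE reports received, and the pharmacovigilance designee assesses their causality and expectedness. A case kept off the SAE form does not enter that review by the route described.

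**Working it through.** No figure in the plan bears on this point, so nothing is recomputed. The check sets the passages side by side.

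**1. Which instruction governs a qualifying event?**

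| Investigator's view of a qualifying liver event | NOTES, 10.2.1 | 8.6.1, 8.6.9 and Appendix 4 | Result |
|---|---|---|---|
| Study intervention suspected | Expedite | Exemption does not apply; SAE reporting if serious | Compatible |
| Judged disease-related, serious | Expedite | Not to be reported as an SAE | Conflict, no rule of precedence |

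Could both instructions in the second row be followed by another route? Section 8.6.5 puts the 24-hour notification of SAEs and AESI on the SAE form, and section 8.6.11 repeats this for AESI. Deaths and pregnancies have forms of their own, but no other expedited channel for adverse events is described. The AESI route would resolve the conflict if liver events were named as AESI for a product, but 8.6.9 makes this possible rather than required, and 8.6.11 leaves the details to the sub-protocol.

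Section 8.3.5 adds a further judgement: laboratory abnormalities associated with the underlying disease are not clinically significant unless the investigator finds them worse than expected. The NOTES contain no such filter.

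**2. Can each limb be evaluated from the required tests?**

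| Element | Required by SoA footnote 4 and Table 10.2.1? |
|---|---|
| ALT, AST | Yes |
| Total bilirubin | Yes |
| Direct bilirubin fraction | No |
| INR | Yes |

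The INR limb can be evaluated in full. For the bilirubin limb, the ALT and total-bilirubin conditions can be checked but the direct-fraction condition cannot. For example, ALT at 5 x ULN with total bilirubin at 2.5 x ULN passes both numerical thresholds (5 > 3 and 2.5 > 2), yet it cannot be said from required data whether the limb is met. One site may order the extra test, another may report without it, and a third may treat the limb as not met.

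**3. Are the enzyme names right?** SGOT is glutamic-oxaloacetic transaminase, the older name for aspartate aminotransferase (AST). SGPT is glutamic-pyruvic transaminase, the older name for alanine aminotransferase (ALT). The table has each the other way round. This rests on standard enzyme nomenclature, since the abbreviation list in Appendix 7 does not link old names to new. Tests are run by local laboratories, so a site whose laboratory reports SGOT and SGPT, and which follows the table, would enter each value in the other's field.

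For the liver rule the swap matters little if either enzyme counts. That is not settled, because AST appears in an open template bracket. It matters where ALT stands alone, as in the list of laboratory adverse events for injectable products in Appendix 3.

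**4. Does the cross-reference lead anywhere?** Section 7.1.1 does not exist, and Appendix 5 only defers. This concerns stopping criteria and follow-up, not the reporting threshold. The brackets left open in the NOTES include the addressee of the report and the AST alternative.

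**The case against.** The strongest reply is that the two reporting instructions can both be obeyed. Section 8.6.9 bars only reporting as an SAE in the eCRF, while the NOTES ask for expedited reporting to the sponsor and name no form. Suspected causation is excepted, and the sub-protocols, which are not shown, may make liver events AESI. This narrows the conflict to qualifying events judged disease-related, but does not remove it: the protocol describes no expedited adverse-event route other than the SAE form, and an optional AESI designation is not a rule of precedence.

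It can also be said that direct bilirubin may be measured as an additional test, and that under section 8.3.5 clinically relevant results from non-required tests must be recorded. That stands. The correct statement is that the limb cannot be *fully evaluated from required data*, not that nobody could ever be shown to meet it.

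Three stronger readings are tempting and are not supported:

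- *The liver rule as a whole cannot be applied.* The INR limb uses only required tests.
- *The sponsor and the data monitoring committee would see liver signals from some sites only.* Liver values are mandatory level I data at every site, and section 8.6.9 has disease-related events recorded systematically in the eCRF. What may differ is expedited reporting and the review it triggers.
- *The trial's ALT and AST summaries will mix two enzymes.* The Schedule of Assessments uses plain ALT and AST, no eCRF label is shown, and the number of sites using the older names is not given.

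The dead reference and open brackets are fairly called editorial, since their content is expressly deferred to the sub-protocols.

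**Conclusion.** Wrong as written, in three respects.

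- Serious liver events that meet the NOTES criteria and are judged disease-related fall under conflicting instructions, with nothing saying which prevails.
- One of the rule's two limbs depends on a measurement outside the required panel.
- The enzyme synonyms in Table 10.2.1 are crossed.

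The consequence is inconsistent expedited reporting, and hence inconsistent safety-group review, of possible severe liver injury, together with a risk of transposed enzyme values at sites that use the older names. The size cannot be stated as a number: the protocol gives no expected rate of such liver events, no share judged disease-related, and no count of sites reporting SGOT/SGPT. No endpoint, randomisation step or efficacy analysis is affected.

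The conclusion assumes that the master-protocol text applies as printed. A sub-protocol that names these liver events as AESI would settle the reporting conflict for that product, but would not by that alone correct the master protocol's laboratory list or its table.

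**What to change.** 1. In Table 10.2.1, correct the synonyms to ALT = SGPT and AST = SGOT, and check that eCRF labels and site guidance did not inherit the error.
2. Reconcile the bilirubin criterion in the NOTES with the required tests in Table 10.2.1 and footnote 4 of the Schedule of Assessments, so that what the rule needs and what is collected agree.
3. Reconcile the NOTES with sections 8.6.1 and 8.6.9 and Appendix 4, so that one stated reporting rule, with a named route, governs events meeting the NOTES criteria, including those judged disease-related.
4. As an editorial matter, replace the reference to section 7.1.1 with one that exists and resolve the template brackets, including the one around AST.

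Which threshold and which reporting rule should apply is for the sponsor's clinical and safety staff; no view is taken here. The cost is an amendment of wording and possibly an eCRF label. If the sponsor chose to add direct bilirubin to the panel, that would mean one further laboratory result at the visits concerned. Sample size and analysis are unchanged.
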